## **1 Introduction:**

The document describes the final data analysis plan for Canadian Cancer Trials Group (CCTG) study SC24.

The trial was centrally activated on July 28, 2015. The first patient was randomized to the trial in Jan. of 2016, and the trial was closure to accrual on Sept 27, 2019 after reaching target sample size. The data has been collected and cleaned by CCTG according to the the group's data management plan.

All analyses will be performed by the trial biostatistician at CCTG and a final statistical analysis report will be prepared. A copy of this report will be sent to the study chair for the writing of the manuscript.

### ***1.1 Study design and objectives***

SC24 is a randomized multicentre phase II/III study. The phase II part is designed to assess feasibility of conducting a phase III trial in the study population, i.e. the ability to accrue 54 patients with spinal metastases to a trial comparing Stereotactic Body Radiotherapy (SBRT) to standard conventional radiotherapy (CRT) over an 18 month period in a Canadian multicentre setting.

Upon successful completion of the phase II portion of the trial, the phase III portion of the trial with primary endpoint of complete pain response at 3 months post-radiation in the target population was initiated.

Patients were randomized to receive either Stereotactic Body Radiotherapy (SBRT) or Standard Conventional Radiotherapy (CRT) in a 1:1 ratio.

Secondary Objectives are:

- Complete pain response in the treatment area t 6 months post-radiation,
- Radiation site progression-free survival (RSS PFS) at 3 and 6 months,
- SINS score at 3 and 6 months,
- Overall survival,
- Adverse event profile,
- Health-related Quality of Life,
- Radiotherapy Quality Assurance (RTQA) compliance.

### ***1.2 Sample Size Determination***

For the randomized phase II portion of the study, a convenience sample size of 54 patients was considered sufficient to evaluate whether accrual is feasible. This sample size would also provide an opportunity to estimate the CRT and SBRT 3 month complete pain relief response rates, which would provide the basis for the sample size calculation of the future randomized controlled trial.

The final sample size for the phase III part was calculated to detect a 20% improvement in 3 month post-radiation in the complete pain response for patients on SBRT arm to the 20% complete

response rate for patients on the CRT arm. Assuming a 15% drop out/inevaluable rate, we expect the complete pain response rates for the intent-to-treat population to be 17% and 34% for the CRT and SBRT arms, respectively. To detect the difference with 80% power using a 2-sided 5% level test, the sample size is 228. The final data set includes all randomized patients including the phase II and phase III trial phases.

### ***1.3 Timing of the Analyses***

The protocol mandated final analysis will be conducted after at least 228 randomized patients have met the projected follow-up period of 6 months post completion of radiotherapy.

This document is to describe the final statistical analysis plan of the final analysis according to the study protocol.

### ***1.4 Data Collection***

Data are collected, entered and managed by CCTG, Kingston, Ontario, according to the group standard data management procedures. The clinical cut-off date will be determined by the date of the 6 month post radiotherapy visit of the last enrolled patient. The database will be locked for analysis after review and resolution of relevant queries.

## **2 Methods and Analyses**

### ***2.1 Analysis Populations***

The analysis populations for this analysis will include both the intention to treat (ITT) population (i.e. all as randomized patients to the treatment arm in each specified population) and the ‘as treated’ population (i.e. all patients who received at least one dose of study treatment).

Analysis of pretreatment characteristics and all efficacy analyses such as complete pain response rate, will be based on the ITT population. Safety and drug exposure analyses will be performed on the as-treated population.

### ***2.2 Conventions for Calculating Key Data***

In general, baseline evaluations are those collected closest, but prior to or on the day of randomization. If pre-randomization assessment was not done, a pre-treatment assessment will be used as baseline assessment.

When either day or month of a date is missing, the missing day and/or month will be imputed by the midpoints within the smallest known interval. For example, if the day of the month is missing for any date used in a calculation, the 15th of the month will be used to replace the missing day. If the month and day of the year are missing for any date used in a calculation, the first of July of the year will be used to replace the missing data.

## 2.3 Analysis Conventions

All comparisons between treatment arms will be carried out using a two-sided test at an alpha level of 5% unless otherwise specified. No formal adjustments will be made for the multiplicity of inferences for multiple clinical endpoints.

The baseline stratification factors that will be used to adjust the analyses where appropriate are listed below:

- Histology (radioresistant vs. radiosensitive)
- “Mass”\* on imaging (present vs. absent)

## 2.4 Randomization and Pre-treatment Characteristics

### 2.4.1 Definitions and Variables

#### 2.4.1.1 Accrual

- Number (%) of randomized patients per study center (Table 1).

#### 2.4.1.2 Randomization/Stratification

- Histology (radioresistant vs. radiosensitive)
- “Mass”\* on imaging (present vs. absent)

(Note: An unknown/missing category will be added to each factor whenever appropriate.) (table 2).

A minimization procedure for treatment assignment was used in this study.

X Baseline patient characteristics will be cross-tabulated with the patient’s corresponding stratification assignment to identify any discrepancies (Table 3)

X Treatment randomized to receive will be compared with the actual treatment received during the first cycle to identify any discrepancies (Table 4)

#### 2.4.1.3 Ineligibility and Major Protocol Violations (Table 5)

X Eligible patients: % yes, no

X Reasons for ineligibility: % for each reason and combination of reasons of ineligibility.

X Major Protocol Violations/deviations: number and % for each type of violation/deviation.

Number and percentage of ineligible patients will be presented by treatment arm.

Reasons for ineligibility: percentage for each reason and combination of reasons of ineligibility will be presented by treatment arm.

The number and percentage of major protocol violations will be presented by treatment arm.

#### 2.4.1.4 Summary of Follow-up

A table showing the median, min and max follow-up (defined as reverse censoring on survival) will be presented for all patients and by treatment group included in the final analysis.

#### 2.4.1.5 Patient Characteristics (Table 7)

- Age: 0-39, 40-49, 50-59, 60-69, 70+, median, min and max;
- Gender (M VS F)
- Primary malignancy (Breast, Lung, GI, GU, Gyn, ...)
- ECOG performance status (0, 1, 2)
- Number of consecutive Spinal segments in target volume (1, 2, 3)
- Worst pain score at target treatment site at baseline (median, min and max)
- Prior spinal surgical/diagnostic procedures for cancer (Y vs N).
- Prior radiation therapy to their spine for cancer (Y vs N).
- SINS score (Median, min, max; mean, std, also by categories: 0-6 vs 7 -12 vs 13 – 18), Epidural Disease Extent (Bilsky scale) (1, 1a, 1b, 1c, 2, 3 ..)
- SINS score by categories of Location, Pain, Bone Lesion, Radiographic Spinal Alignment, Vertebral Body Collapse, and Posterolateral Involvement. (Median, min, max; mean, std).
- Angular Kyphosis (degrees) (0, 1, 2...),
- Opioid medications reported in the last 24 hours (Median, min and Max, mean, std)
- bisphosphonates or other bone targeted therapy ( Y vs. N).

\*An unknown category will be added when appropriate.

#### 2.4.1.7 Baseline Adverse Events (table 8)

Baseline adverse event were collected within 7 days prior to randomization, and summarized according to NCI CTCAE V4.0.

#### 2.4.1.8 Baseline NON-opioid Medications (table 9)

A NON-opioid medication which was taken within 24 hours prior to ghe baseline assessment.

- X Any NON-opioid medication: % yes, no
- X Number of patients for each type of medication.

#### 2.4.1.9 Baseline Cancer Treatment (Table 10)

Number and percent of patients received cancer treatment within 30 days prior to randomization will be summarized by treatment arm.

## **2.4.2 Analysis of pre-treatment characteristics**

No formal statistical tests will be performed to assess the homogeneity of baseline characteristics between the arms. Categorical variables will be tabulated by treatment arm and for all patients. Continuous variables (e.g., age) will be presented using summary statistics (n, median, min and max) or specified cutoff categories by treatment arm and for all patients. Analyses will be based on all randomized patients by arm based on the ITT population.

## **2.5 Efficacy**

### **2.5.1 Definitions and Variables**

#### **2.5.1.1 Complete pain response in the treatment area at 3 months post-radiation**

All patients who have received at least one dose of radiotherapy and provide complete worst pain score information for the treated site of radiation treatment and opioid analgesic intake information at baseline and at least the 3 month follow up contact will be considered evaluable for response to radiotherapy.

A Complete Pain Response is defined as a pain score of zero (0) at the treated site with no concomitant increase in analgesic intake (stable or reducing analgesics in daily oral morphine equivalent). The response status at 3-month and 6-month will be derived by comparison of worst pain score and analgesic intake at the time point to baseline data. As a sensitive analysis, the response status will be derived from comparison of worst pain score and analgesic intake at the time point to day 0 data prior to RT, and perform the similar analyses.

#### **2.5.1.2 Response to radiation therapy (CR/PR)**

Pain response to radiotherapy is based on the International Bone Metastases Consensus Endpoint definitions and will be measured at 3 months assessment.

A complete Pain Response is defined as a pain score of zero (0) at the treated site with no concomitant increase in analgesic intake (stable or reducing analgesics in daily oral morphine equivalent)

A partial response is defined as any of the following:

- i. Reduction in worst pain score of two or more at the bony metastatic site on a 0–10 scale without analgesic increase.
- ii. Analgesic reduction of 25% or more from baseline without an increase in worst pain score with reference to baseline.
- iii. For patients who were using opioid analgesics at the baseline assessment, a daily oral morphine equivalence of zero (0) without an increase in worst pain score relative to the baseline worst pain score.

### **2.5.1.3 Pain Progression (PD) and Stable pain (SD)**

Pain progression is defined as any of the following:

- i. An increase in worst pain score of two or more points above baseline at the treated site without reduction of analgesic use.
- ii. An increase of 25% or more in daily oral morphine equivalent compared with baseline, without reduction in worst pain score.
- iii. For patients who were not using opioid analgesics at the baseline assessment (daily oral morphine equivalence = 0), consumption of any opioid analgesic without a reduction in worst pain score relative to the baseline worst pain score.

*Stable pain (SD) is assigned to the remaining evaluable patients, who do not meet any of the categories of Complete/Partial Response and Pain Progression.*

### **2.5.1.4 Complete pain response in the treatment area at 6 months post-radiation**

All patients who have received at least one dose of radiotherapy and provide complete worst pain score information for the treated site of radiation treatment and opioid analgesic intake information at baseline and at least the 6 month follow up contact will be considered evaluable for response to radiotherapy.

A Complete Pain Response is defined as a pain score of zero (0) at the treated site with no concomitant increase in analgesic intake (stable or reducing analgesics in daily oral morphine equivalent).

### **2.5.1.4 Radiation site progression-free survival (RSS PFS) at 3 and 6 months**

Radiation site progression free survival is defined as the time from randomization to local progression or death. For patients who did not reported progression of disease and alive will be censored at the last disease evaluation time. It is based on the center investigator reported data.

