10.2.2 Radiation Site Progression Free Survival (RSS PFS)

Radiation site progression free survival is defined as the time from randomization to local progression or death.

The response assessment will be an investigator interpretation of the following criteria: lesion status, size, epidural disease extent (Bilsky scale and 3 D measurements), degree of angular kyphosis and height of vertebral body [[name] 2015].

Local progression may be defined as:

- Gross unequivocal increase in tumor volume or linear dimension.
- Any new or progressive tumor within the epidural space.
- Neurologic deterioration attributable to pre-existing epidural disease with equivocal increased epidural disease dimensions on MRI.

Biopsy is recommended in those situations in which pseudoprogression due to radiation reaction cannot be ruled out.

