13.2 Central Radiology Review

Central radiology review for the purposes of the radiation site progression-free survival (RSS PFS) secondary endpoint will be required for all patients randomized to the study. The central reviewer will be blinded to study radiotherapy treatment allocation. Please see the SC.24 trial webpage (www.ctg.queensu.ca) for details of electronic upload of MRI files.

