14.6 Secondary Endpoint and Analysis

Complete pain response in the treatment area at 6 months post-radiation. All analyses for the primary endpoint will be performed for the complete pain response at 6 months post-radiation.

AMEND #1: 2017-FEB-02; AMEND #2: 2018-APR-03; AMEND #3: 2018-OCT-31

Radiation site progression-free survival (RSS PFS) is defined as the time from the date of randomization to the date of documented local progression, as defined in Section 10.2.2; or the date of death. Patients who have not progressed or died by the cutoff date of final analysis, RSS PFS will be censored on the date of the last disease assessment. A Kaplan-Meier curve for proportions of RSS PFS in each treatment arm will be displayed. The RSS PFS rates at 3 and 6 months and their 95% confidence intervals will be estimated. The 95% confidence intervals for the medial RSS PFS will be computed using the method of Brookmeyer and Crowley. The difference in distributions of RSS PFS in the two treatment arms will be compared using the log-rank test stratified by the stratification factors at randomization except study centre. Other potential important factors that predict RSS PFS will be assessed using Cox regression. Overall survival will be analysed similarly.

The incidence of acute severe adverse incidences for each arm will be calculated with its 95% confidence interval, and the analyses will be performed in a tiered comparison, i.e., comparing the overall incidence rates between treatment arms first, then comparison of radiotherapy and disease related symptoms and compared by means of Chi-square analysis or Fisher exact test.

SINS scores will be summarized for data at baseline, 3 and 6 months evaluations. The potential prognostic effects of baseline SINS score on the complete pain response at 3 months post-radiation and the overall survival will be explored using logistic and Cox regression models respectively.

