### **2.5.2.3 Radiation site progression-free survival (RSS PFS) at 3 and 6 months**

K-M estimate of RSS PFS distribution will be displayed by treatment arm (Figure 1), and log-rank test stratified by stratification factors of Histology (radioresistant vs. radiosensitive) and “Mass” on imaging (present vs. absent) will be used to test the difference and Cox regression model stratified by the stratification factors will be used to estimate the HR and its 95% C.I. (table 19). The 3 months and 6 months RSS PFS rate and its variance will be estimated from the K-M curves by treatment arm.

**Subgroup analysis:** RSS PFS will be performed based on patients’ stratification factors at baseline, i. e. Histology (radioresistant vs. radiosensitive) and “Mass”\* on imaging (present vs. absent) (Table 20) with interaction p-value to tell if any differential treatment effect across levels of stratification factors.

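### The protocol requires an arm-blinded central MRI review of every randomized patient for RSS PFS, but no section gives that read a role and the SAP plans no analysis of it

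*SAP*

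**What the plan says.** Protocol 13.2 sets up the review and ties it to this endpoint: "Central radiology review for the purposes of the radiation site progression-free survival (RSS PFS) secondary endpoint will be required for all patients randomized". It adds: "The central reviewer will be blinded to study radiotherapy treatment allocation".

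Protocol 10.2.2, which defines RSS PFS, names a different reader: "The response assessment will be an investigator interpretation of the following criteria". Two of its provisions acknowledge uncertain images. The third progression criterion is "Neurologic deterioration attributable to pre-existing epidural disease with equivocal increased epidural disease dimensions on MRI", and the section closes with "Biopsy is recommended in those situations in which pseudoprogression due to radiation reaction cannot be ruled out".

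Protocol 14.6 takes the event to be "the date of documented local progression, as defined in Section 10.2.2; or the date of death" and does not mention the central read.

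SAP 2.5.1.4 names one data source: "It is based on the center investigator reported data". SAP 2.5.2.3 then plans Kaplan-Meier curves, a log-rank test and a Cox model stratified by histology and mass, and subgroup analyses. Tables 19 and 20 are the shells. All of these draw on that single source.

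**The concern.** The treatment schema describes the trial as non-blinded, and nothing in the documents keeps the site reader from knowing the arm. Progression at an irradiated vertebra can be hard to call, and the protocol itself allows for equivocal change and for pseudoprogression. A reader's expectations can therefore enter the read, and they may differ between a stereotactic and a conventional arm. An arm-blinded review of every patient is the natural check, and the protocol already requires one.

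Under the plan as written, the between-arm RSS PFS comparison would be reported without that check, and readers would not learn whether the two reads agree. If the role of the central read is settled only after results are known, using it or leaving it out becomes a post hoc choice.

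**Working it through.** **1. The sections side by side**

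| Place | Whose read | Role of the central read |
|---|---|---|
| Protocol 10.2.2 (definition) | Investigator | Not mentioned |
| Protocol 13.2 (review procedure) | Central, arm-blinded, all randomized patients | Done for RSS PFS; use not stated |
| Protocol 14.6 (analysis) | Refers to 10.2.2 | Not mentioned |
| SAP 2.5.1.4 (definition) | Centre investigator | Not mentioned |
| SAP 2.5.2.3, Tables 19-20 | Centre investigator (from 2.5.1.4) | No analysis, no comparison |

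No section says whether the central read replaces, confirms, adjudicates or supplements the site read, or what happens when they differ. The ambiguity starts inside the protocol, between 10.2.2 and 13.2. The SAP settles the data source but makes no provision for the blinded read.

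**2. The plan's own figure**

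The documents give no power, event count or disagreement rate for RSS PFS. Their only powered figure is the total of 228 for the pain endpoint. The continuity-corrected two-proportion formula (17% vs 34%, two-sided 5%, 80% power) reproduces it at 114 per arm. It is used below only for the arm size.

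**3. How much could arm-dependent reading matter? (illustration; every rate is assumed)**

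Model: 114 per arm, no true difference, exponential local failure and death, 65% one-year local control, 25% six-month mortality. Scans are at 3.5 and 6.5 months from randomization, and progression is dated at the scan. There are four strata (25% radioresistant, 50% with mass, each multiplying both hazards by 1.5). The test is a stratified log-rank, two-sided 5%. Over-calling is the chance per scan of calling progression where there is none. The base case has 4,000 replicates (Monte Carlo SE 0.3 to 0.7 points). The grid uses local control of 45, 65 and 80% by mortality of 15, 25 and 35%, with 2,000 replicates per cell.

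| Over-calling, arm A vs arm B | Type I error, base case | Range over grid |
|---|---|---|
| 5% vs 5% | 5.1% | not run |
| 7% vs 5% | 6.1% | 4.4 to 6.9% |
| 10% vs 5% | 10.9% | 8.1 to 18.4% |
| 15% vs 5% | 28.3% | 17.6 to 46.6% |

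Reversing the arms gives similar figures (5% vs 10%: 12.1%; 5% vs 15%: 29.0%). Raising over-calling in an arm from 5% to 15% moves its first events from 25.6 progressions and 28.1 deaths to 38.8 progressions and 27.0 deaths.

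The 45 to 80% range is an assumption. Protocol 2.1 gives 45% at one year for bulky tumours after conventional radiotherapy. Protocol 2.2 gives about 80% from single-arm stereotactic series with no time point. Neither is a one-year figure for this trial's population.

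**4. What an agreement table could show**

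For disagreement proportions p and q with n reads per arm, SE = √[(p(1−p) + q(1−q))/n]. The chance that the 95% CI excludes zero is about Φ(|p−q|/SE − 1.96).

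- n = 114 × 0.85 ≈ 97. This borrows the 15% loss that the protocol assumes for the pain endpoint; no MRI figure is given.
 - 15% vs 5%: SE = √(0.175/97) = 0.0425; 0.10/0.0425 = 2.35; Φ(0.39) ≈ 65%.
 - 10% vs 5%: SE = √(0.1375/97) = 0.0377; 0.05/0.0377 = 1.33; Φ(−0.63) ≈ 26%.
- n ≈ 85, those alive at six months under the assumed mortality (114 × 0.75 = 85.5).
 - 15% vs 5%: SE = √(0.175/85) = 0.0454; 0.10/0.0454 = 2.20; Φ(0.24) ≈ 60%.

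The table would miss even a large gap in about a third of trials or more, so it is descriptive only.

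**The case against.** The strongest reply is that nothing has been breached. Protocol 10.2.2 makes progression an investigator judgement, 14.6 points to it, and SAP 2.5.1.4 follows both. Protocol 13.2 asks for a review, not for a second analysis, an agreement table or adjudication. The review may have served some operational purpose, such as querying site reports; the documents neither show nor exclude that. An imaging read also cannot reproduce the third criterion in 10.2.2, which needs neurologic findings. All of this stands. It rules out calling the SAP non-compliant and limits the request to a clarification and a supportive analysis. It does not supply the missing role for a review that the protocol ties to this endpoint.

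A second reply is that the over-calling rates are invented and SAP 2.3 makes no multiplicity adjustment across endpoints, so a type I error figure for one secondary test carries limited weight. That also stands. The figures show when reading differences would matter, not that they occurred.

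A reader might infer from SAP 2.6.2 that a two-source table layout is already in place, since that section says radiotherapy compliance is reported from both centre and central review. The shells do not bear this out: Tables 27 and 28 have compliance-rating columns and no label for the source.

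**Conclusion.** The point holds as a gap. A mandatory, arm-blinded read, collected for RSS PFS in every randomized patient, has no stated role and no planned output, in an open-label trial whose progression criteria need judgement.

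Three stronger readings are tempting and unsupported. First, that the SAP contradicts the protocol: it follows 10.2.2. Second, that the RSS PFS comparison is biased: no over-calling or disagreement rate appears in the documents, so the size and direction are unknown, and a gap as small as 7% vs 5% leaves the type I error near nominal in the illustration. Third, that comparing the two reads would reliably expose a differential: at 15% vs 5% disagreement the chance is only about 60 to 65%.

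The inflation to about 28% rests on an assumed 15% vs 5% over-calling gap and on the assumed event rates. The textual finding needs no assumption. Severity is minor to moderate: RSS PFS is a secondary endpoint, and the primary pain analysis, the sample size and overall survival are untouched.

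**What to change.** 1. State the role of the central read, reconciling protocol 10.2.2 with 13.2.
2. Keep the centre-investigator analysis as the main RSS PFS analysis.
3. Add to SAP 2.5.2.3 a pre-specified supportive analysis that repeats Table 19 (Table 20 if wanted), with imaging progression taken from the blinded central read and death as an event.
4. Fix in advance how site-reported neurologic progression and biopsy results are counted when they conflict with the central read. First check whether the Relapse / Progression Report in protocol Appendix IV records which 10.2.2 criterion was met; the documents do not show this.
5. Add one descriptive table of agreement between the two reads at 3 and 6 months by arm, with the number of completed central reads.

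The cost is some SAP wording, one repeated table and one new one. No new scans are needed, since MRI at 3 and 6 months and the review are already required. The SAP introduction says data have been collected and cleaned, but nothing shows that the central reads are complete or in the database. Outstanding reads may need to be finished or entered before the lock described in SAP 1.4. Neurologic progression would still rest on unblinded site judgement.
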